## 15.1 Primary Analysis

An Analysis of Variance (ANOVA) of the baseline  $\log_{10}$  CFU/cm^2 values will be performed separately for abdomen and inguen to determine whether the randomization resulted in treatment arms with similar treatment day baseline CFU/cm^2 values.

The primary purpose of the study is to compare the immediate antimicrobial activity of the Investigational Products to the Negative Control and Active Control according to the methods described in the FDA TFM using the statistical analyses outlined in the deferral letters published by the FDA on January 19, 2017. A linear regression model will be used for primary analysis. In the model, the response is the post-treatment  $\log_{10}$  bacterial counts and predictors are the treatment effect and the pre-treatment  $\log_{10}$  bacterial counts as a covariate. The interaction between the treatment and pre-treatment  $\log_{10}$  bacterial counts will also be explored. If there is no significant interaction detected between treatment and pre-treatment  $\log_{10}$  bacterial counts, the interaction term will be removed from the model and the average difference between treatments will be estimated from the linear regression model after correcting for pre-treatment  $\log_{10}$  bacterial counts. If there is a significant interaction detected between treatment and pre-treatment  $\log_{10}$  bacterial counts, the average difference between treatments will be estimated from the linear regression model after averaging over the interaction term. The objective is to achieve a mean treatment effect ( $\log_{10}$  reduction) for Investigational Products no less than that for the Active Control by more than 0.5  $\log_{10}$  and at least 1.2  $\log_{10}$  greater than that for the Negative Control on both the abdomen and inguen. The 95% confidence intervals will be summarized for each product tested, grouped by anatomical site and each post-application time point (30 seconds and 10 minutes) and compared to the non-inferiority margin of 0.5  $\log_{10}$  for Investigational Products vs. Active Control and compared to the superiority margin of 1.2  $\log_{10}$  for Investigational Products vs. Negative Control.

It is expected that the treatment effects will meet the standards outlined above, however this is a Phase II study to inform design of future efficacy studies and is not designed to provide statistically powered evidence of efficacy.

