3.3 Study Design

This is a single-center and randomized design where each subject receives two different treatments out of 4 treatments, one on the left side of the body and one on the right side. This means there are 6 possible combinations of treatments (assuming A, B and C are either Investigational Product #1, Investigational Product #2 or Active Control, D is the Negative Control): A & B, A & C, A & D, B & C, B & D, and C & D.

A minimum of 72 evaluable subjects will be required to achieve a total of at least 144 test sites for groin and abdominal regions. To achieve 36 evaluable test sites from Investigational Product 1, Investigational Product 2, Active Control and Negative Control arms for groin and abdominal regions, of the minimum 72 evaluable subjects:

- 12 subjects will receive treatments from both A and B.
- 12 subjects will receive treatments from both A and C.
- 12 subjects will receive treatments from both A and D.
- 12 subjects will receive treatments from both B and C.
- 12 subjects will receive treatments from both B and D.
- 12 subjects will receive treatments from both C and D.

The two investigational products and the active control will be randomly assigned codes of A, B or C. However, due to visual differences between each of the test materials, the products cannot be blinded to all study staff. In order to guard against any bias of the study outcome, technicians who participate in product application or sample collection from subjects during treatment day procedures will not participate in the processing of samples. The technicians processing samples and/or counting the resultant plates will be blinded to the study randomization during the data gathering processes. Plate counts will be reviewed and recorded by separate BSLI staff prior to being entered into a data spreadsheet where product information (unblinding) would occur.

Subjects will be sampled for treatment day baseline microbial populations on randomly assigned sites of the abdominal and inguinal areas on both sides. Subjects will have samples collected at baseline, 30 seconds (± 5 seconds), 10 minutes (± 30 seconds) and at 6 hours (± 30 minutes) post-treatment application on both abdomen and inguinal sites. All sampling times will be calculated from the completion of the dry time of each product following application.

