7.3 Analysis Methods

For each body site, when per-protocol data are different from mITT data for average treatment effect (ATE), responder rate, log reduction or product expression volumes, per-protocol analysis and mITT analysis will be performed separately using the same statistical methods. The following analysis methods will be applied to both per-protocol analysis and mITT analysis, both abdomen and groin.

An alpha level of 5% (two-sided) is used for all analyses.

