7.3.1 Primary Analysis

The primary purpose of the study is to compare the immediate antimicrobial activity of the Investigational Products to the Negative Control and Active Control according to the methods described in the FDA TFM with the statistical analyses outlined in a deferral letter published January 19, 2017. There are two test criteria that drive the hypotheses.

- Evaluate the average treatment effect (ATE) of the Active Control (AC) compared to each Investigational Product (IP) at 30 seconds and 10 minutes for non-inferiority on both abdomen and groin. ATE of the AC compared to either IP is defined as the contrast of the treatment effect of the IP minus the treatment effect of the AC (IP - AC) in the linear regression. Statistical hypotheses are:
 - Ho: The upper bound 95% confidence interval of the ATE of IP - AC $\geq 0.5 \log_{10}$
 - Ha: The upper bound 95% confidence interval of the ATE of IP - AC $< 0.5 \log_{10}$
- Evaluate the Average Treatment effect (ATE) of each Investigational Product (IP) compared to the Negative Control (NC) at 30 seconds and 10 minutes on both abdomen and inguen anatomical area. ATE of the IP compared to the NC is defined as the contrast of the treatment effect of the NC minus the treatment effect of the IP (NC - IP) in the linear regression. Statistical hypotheses are:
 - Ho: The lower bound 95% confidence interval of the ATE of NC - IP $\leq 1.2 \log_{10}$
 - Ha: The lower bound 95% confidence interval of the ATE of NC - IP $> 1.2 \log_{10}$

Ho is the null hypothesis and Ha is the alternative hypothesis.

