A linear regression model for each body site will be used for primary analysis. In the model, the response is the post-treatment \log_{10} bacterial counts and predictors are the treatment effect as a fixed effect and the pre-treatment \log_{10} bacterial counts as a covariate. The interaction between the treatment and pre-treatment \log_{10} bacterial counts will be also explored. If there is no significant interaction detected between treatment and pre-treatment \log_{10} bacterial counts, the interaction term will be removed from the model and the average difference between treatments will be estimated from the linear regression model after correcting for pre-treatment \log_{10} bacterial counts. If there is a significant interaction detected between treatment and pre-treatment \log_{10} bacterial counts, the average difference between treatments will be estimated from the linear regression model at the average of the covariate. Additional factors (e.g., technician and subject demographics) may be also included in the model and the effects will be investigated.

Since the study will declare success when and only when both non-inferiority and superiority are demonstrated for both abdomen and groin, no multiplicity adjustment for multiple primary objectives is required.

An example for results of comparisons above can be found in Tables 5 and 6. All results that do not meet the targets are highlighted.

Table 5: Example: ATE for IP1/IP2 - AC for Groin

Comparison	Time Point	N Pairs	Difference in ATE	Conf Int	Meet Non-inferiority Criteria
IP1 - AC	30 Seconds	36	-0.50	-1.31, 0.30	Yes
IP2 - AC	30 Seconds	36	-0.35	-1.00, 0.31	Yes
IP1 - AC	10 Minutes	36	0.32	-0.52, 1.15	No
IP2 - AC	10 Minutes	36	0.50	-0.39, 1.39	No

Table 6: Example: ATE for NC - IP1/IP2 for Groin

Comparison	Time Point	N Pairs	Difference in ATE	Conf Int	Meet Superiority Criteria
NC - IP1	30 Seconds	36	1.35	1.01, 1.59	No
NC - IP2	30 Seconds	36	1.23	0.90, 1.50	No
NC - IP1	10 Minutes	36	0.4	0.02, 0.82	No
NC - IP2	10 Minutes	36	1.6	1.28, 1.91	Yes

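### The primary regression makes no provision for unequal arm variances, so saline residuals enter the IP - AC interval; the direction and size of the error depend on arm SDs and a within-subject correlation that the documents do not give

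*SAP*

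**What the plan says.** SAP 7.3.1 states "A linear regression model for each body site will be used for primary analysis"; Protocol 15.1 has the same sentence without the body-site qualifier ("A linear regression model will be used for primary analysis"). In the SAP the "predictors are the treatment effect as a fixed effect", and the baseline log10 count is a covariate. A treatment-by-baseline interaction is examined and dropped if not significant.

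Both decision criteria are read from contrasts in this regression. Non-inferiority is judged on "The upper bound 95% confidence interval of the ATE of IP - AC", and superiority on the lower bound for NC - IP. Protocol 15.1 has the intervals "compared to the non-inferiority margin of 0.5" log10 for the active control and "compared to the superiority margin of 1.2" log10 for saline. SAP 7.3 adds: "An alpha level of 5% (two-sided) is used for all analyses". Each bound is therefore a one-sided 2.5% test.

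I found no arm-specific variance, robust standard error, variance check or fallback in either document. The primary model has no subject term, although SAP 3.3 gives each subject two treatments, one per side. SAP 7.3.3.3 does use a random subject effect, but only for product expression.

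**The concern.** Saline is not part of the IP - AC contrast. In a single four-arm fit with a common residual variance and equal arm sizes, it still supplies a quarter of the variance behind that contrast's standard error. Saline counts should stay near baseline, within the 2.5-log mITT baseline window, and the covariate may explain more of their spread. Treated counts also depend on how much kill is achieved, which can vary between sites. Unequal residual variances are therefore plausible.

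If the treated arms are the more variable, pooling shortens the IP - AC interval and lengthens the NC - IP interval. A shortened IP - AC interval raises the chance of a false non-inferiority conclusion. SAP 7.3.1 attaches a success rule to these intervals, and its Tables 5 and 6 give a Yes or No for each comparison. The study is also meant to inform later efficacy trials, for which arm-specific spread is a basic input that a pooled estimate hides.

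**Working it through.** **Design count (reproduced).** SAP 3.3: "To achieve 36 evaluable test sites from Investigational Product 1, Investigational Product 2, Active Control and Negative Control arms". Six treatment pairs × 12 subjects = 72 subjects. Each treatment is in three pairs, so 3 × 12 = 36 sites per arm, and 72 × 2 = 144 sites per body site. Any two given arms share 12 subjects. No planning SD or power is stated, so there is none to reproduce.

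**Assumptions.** One fit per body site and time point (the SAP does not state how time points are handled). The three treated arms share a residual SD s_t after baseline adjustment; saline has s_n. Residual degrees of freedom are 144 - 5 = 139, t = 1.977. The SD ratios below are assumed, not taken from the trial.

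**Independent residuals.**
- Pooled variance: p = (3·s_t² + s_n²)/4
- SE² used by the model for every contrast: 2p/36
- True SE², IP - AC: 2·s_t²/36
- True SE², NC - IP: (s_t² + s_n²)/36
- Model/true SE: √p / s_t for IP - AC, and √[2p/(s_t² + s_n²)] for NC - IP
- One-sided error: Φ(-1.96 × SE ratio)

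Example, s_t = 1 and s_n = 0.5: p = 3.25/4 = 0.8125. IP - AC: √0.8125 = 0.901, error Φ(-1.767) = 3.9%. NC - IP: √(1.625/1.25) = 1.140, error 1.3%.

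| s_n/s_t | IP - AC SE ratio | one-sided error | coverage | NC - IP SE ratio | one-sided error |
|---|---|---|---|---|---|
| 0.75 | 0.944 | 3.2% | 93.6% | 1.068 | 1.8% |
| 0.65 | 0.925 | 3.5% | 93.0% | 1.097 | 1.6% |
| 0.50 | 0.901 | 3.9% | 92.3% | 1.140 | 1.3% |
| 0 (limit) | 0.866 | 4.5% | 91.0% | 1.225 | 0.8% |

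The last row is a bound: with three treated arms to one saline arm, the IP - AC standard error cannot be more than about 13% too small.

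**With left/right correlation.** Let the residuals of a subject's two sides have correlation ρ. The covariance of two treated arm means is 12·ρ·s_t²/36², so the true IP - AC variance is (2·s_t²/36)(1 - ρ/3). The narrowing is cancelled when 1 - ρ/3 = p/s_t², that is ρ = 3(1 - SE ratio²). This gives 0.33, 0.43 and 0.56 for SD ratios 0.75, 0.65 and 0.50.

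Simulation of the 72-subject layout (baseline covariate, 6,000 runs per case) agrees:

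| s_t, s_n | contrast | ρ = 0 | ρ = 0.3 | ρ = 0.6 |
|---|---|---|---|---|
| 1, 0.65 | IP - AC coverage | 93.0% | 94.5% | 95.3% |
| 1, 0.5 | IP - AC coverage | 92.6% | 94.0% | 95.4% |
| 1, 0.5 | NC - IP coverage | 97.2% | 97.9% | 98.4% |

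**If saline is the more variable arm.** Take s_t = 0.6 and s_n = 1: p = (1.08 + 1)/4 = 0.52. IP - AC SE ratio = 0.721/0.6 = 1.20, too wide. NC - IP SE ratio = √(1.04/1.36) = 0.874, too narrow. Simulated at ρ = 0, coverage is 98.0% for IP - AC and 92.0% for NC - IP, with a superiority error of about 4%.

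**The case against.** **The direction is not established.** A reader might infer from the SAP's example Table 8 that treated counts are more variable, since rows with means near 5.8 to 5.9 have SDs of 0.53 to 0.54 and rows with means near 3 have 0.72 to 1.10. The table cannot carry that. Read by arm, saline (D) at 30 seconds has SD 1.09, against 1.10, 0.89 and 0.72 for A, B and C. The same row of values appears under A baseline, B 10 minutes and D 10 minutes. B has a groin baseline minimum of 0.00, although SAP 6.1 requires 5.00 to 7.50. These are placeholders. In addition, SAP 7.1.1 sets counts below 1 CFU/cm² to 0 log10, which can compress treated-arm spread, particularly on the abdomen, where baselines start at 3.00. This objection stands: the direction is an assumption.

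**Pooling is inferred.** The SAP does not use the words common variance. The half-widths in Tables 5 and 6 (about 0.66 to 0.89 for IP - AC, 0.29 to 0.40 for NC - IP) could not come from one pooled fit with equal arms. They are labelled as examples too, so they settle nothing. An ordinary regression with treatment as a factor remains the natural reading.

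**Pairing offsets the harm.** This is right for IP - AC and limits the claim. But it is one omission compensating for another at an unknown correlation, and it does not validate the interval. Adding a subject effect while still pooling the variance left the simulated non-inferiority error at 2.8% to 4.4% over twelve settings (treated/saline SDs 1.10/0.53, 1.0/0.5 and 0.9/0.6; ρ from 0 to 0.6).

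**The consequence is small.** The study is Phase II, is stated not to be powered for efficacy, and requires both criteria on both body sites. That lowers the priority. It does not remove the issue: a product well clear of saline, and borderline against the active control at one site only, is protected there only by the IP - AC bound.

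**Conclusion.** The concern holds in a conditional form. As naturally read, the plan takes both contrasts from one residual variance over four arms and has no safeguard if the variances differ.

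- **Treated arms more variable, independent residuals, saline/treated SD ratio 0.5 to 0.75:** the IP - AC standard error is about 6% to 10% too small, with a non-inferiority error of about 3.2% to 3.9% (limit about 4.5%). The NC - IP standard error is about 7% to 14% too large.
- **Positive within-subject correlation as well:** the IP - AC shortfall shrinks and is gone at a correlation of about 0.3 to 0.6. NC - IP stays too wide.
- **Saline more variable:** the directions reverse, and it is the superiority test that becomes anti-conservative, at about 4% for SDs of 0.6 and 1.0.
- **Equal SDs:** pooling does no harm.

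A reader might go further and infer that the planned non-inferiority test is known to be anti-conservative. The documents do not support that, because they give neither real arm SDs nor a within-subject correlation. What they do support is that the error rate of the two decision bounds rests on an unstated equal-variance assumption that is easy to avoid.

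**What to change.** Keep the mean model and the IP - AC and NC - IP contrasts. Add one sentence to SAP 7.3.1 so that the Table 5 and 6 intervals come from either:

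- a robust covariance clustered on subject with a small-sample correction (for example CR2 or CR3); or
- a mixed model, `lme` with a random subject effect and `weights = varIdent(form = ~1 | treatment)`.

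Either option handles unequal variances and left/right pairing together, without knowing in advance which arm is noisier. In simulation, subject-clustered robust errors kept the one-sided error at 2.0% to 2.7% in all nine settings tried. Arm-specific variances or HC3 alone would leave the pairing ignored and turn conservative (1.3% to 1.7% at a correlation of 0.6). The same sentence should say whether the model is fitted separately at each time point.

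Cost: if treated arms are noisier, non-inferiority intervals widen somewhat. At s_t = 1, s_n = 0.5 and independent residuals, the IP - AC half-width goes from 0.420 to 0.466 log10 and the NC - IP half-width from 0.420 to 0.368. If the SDs are equal and the within-subject correlation is negligible, results barely change. No change to design or sample size is needed.

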### **13.3 Randomization**

The randomization scheme for the study will be provided by the Study Sponsor. The test materials will be coded as A, B, C, and D and assigned randomly to the subjects per a computer-generated randomization schedule in blocks of 24 subjects. Subjects will be randomized to test all of the Treatment Groups.

Each subject will receive two different treatments, one on the right side of the body and one on the left. The 6 possible combinations for product application is as follows:

- Treatment A / Treatment B
- Treatment A / Treatment C
- Treatment A / Treatment D
- Treatment B / Treatment C
- Treatment B / Treatment D
- Treatment C / Treatment D

A minimum of 72 evaluable subjects will be required to achieve 36 evaluable test sites for each test material: Investigational Product #1, Investigational Product #2, Active Control, and Negative Control arms for inguinal and abdominal regions (at least 144 total test sites for inguinal and abdominal regions).

Subjects will be randomized to treatment using the following block design:

- The study product assignments will be balanced such that the number of readings per anatomical site matches the calculated requirements.
- The application will be randomized so that each treatment is used on an equal number of left and right sides of the body.
- Each inguinal and abdominal sample site is divided into four areas, and all four of the areas are sampled: one at baseline, one at 30 seconds, one at 10 minutes, and one at 6 hours. Therefore, for any inguen or abdomen site there are 24 possible sampling orders.

The number of subjects required for a completely balanced block design for all factors at once (study products, left/right, and sampling order) is a multiple of 288 (6\*2\*24). The number of intended subjects makes it infeasible to provide a completely balanced block design, so the following priority order will be used for design:

1. Treatment combinations will be applied in balanced blocks
2. Left/right balance will be preserved – each treatment will be applied an equal number of times to each side of the body.
3. Sampling orders will be assigned in blocks of 24 as much as possible. If the final number of subjects is not a multiple of 24 the remaining subjects will be assigned random non-duplicate sample orders from the 24 possible sample orders.

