7.3.3.3 Product Expression Volumes/Weight

An analysis of variance (ANOVA) of the applied volumes/weight will be performed separately for each body site based on mITT data and/or per-protocol data. In the model, there will be a random subject effect, a fixed body side (left or right) effect, a fixed treatment effect and the interaction between fixed effects. ANOVA table will be checked to see whether the treatment has a significant effect on product expression volumes as well as the interaction. If a significant difference is found, subgroup comparisons with Tukey’s method will be made to determine which pair of comparisons shows significant difference.

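### The primary model omits body side and sampling position, two of the three factors the randomisation balances; this costs some precision if either affects counts, but causes no bias

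*SAP*

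**What the plan says.** Protocol 13.3 names the factors it would like to balance fully: "The number of subjects required for a completely balanced block design for all factors at once (study products, left/right, and sampling order"), which would need a multiple of 288 subjects. With about 72 it ranks them. Treatment combinations come first. Side comes second: "each treatment will be applied an equal number of times to each side of the body". Sampling order comes third: "Sampling orders will be assigned in blocks of 24 as much as possible". Position arises because "Each inguinal and abdominal sample site is divided into four areas, and all four of the areas are sampled", one at baseline and one at each post-treatment time. The section adds that blocking will be adjusted to the final numbers to come as close as it can to joint balance on the three factors.

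The primary model in SAP 7.3.1 is a linear regression for each body site whose "predictors are the treatment effect as a fixed effect and the pre-treatment" log10 count, with the treatment-by-baseline interaction explored. Protocol 7.1 and 15.1 describe the same model. SAP 7.3.1 then says: "Additional factors (e.g., technician and subject demographics) may be also included in the model and the effects will be investigated".

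By contrast, the exploratory model for product weight (SAP 7.3.3.3) has a random subject effect and "a fixed body side (left or right) effect, a fixed treatment effect and the interaction between fixed effects".

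**The concern.** A factor built into the randomisation normally goes into the analysis. If left and right sides differ in recoverable flora, or the four areas within a site do, that variation falls into the residual of the planned model. It then widens the IP - AC interval read against 0.5 log10 and the NC - IP interval read against 1.2 log10. The study is meant to inform later efficacy trials, so an inflated residual variance could also carry into their sample size. The optional sentence does not settle the matter: it names neither factor, and it does not say when a factor enters or which fit is compared with the margins.

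**Working it through.** **1. The plan's own counts.** Four products give 6 pairs. 6 × 12 = 72 subjects, × 2 sides = 144 sites per region. Each product is in 3 pairs, so 3 × 12 = 36 sites. Full balance needs 6 × 2 × 24 = 288. All agree with the documents. A block of 24 holds 24/(6 × 2) = 2 subjects per pair and left/right arrangement, so each product falls on 18 left and 18 right sites as randomised.

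**2. Position balance.** The expected count is 36/4 = 9 sites per position per product. If orders are dealt within each block independently of product (an assumption), the largest difference between two arms in 30-second position counts has median 5 and 95th percentile 9 sites. Exact balance is also attainable. The 24 orders split into six sets of four in which each position occurs once at each time. One set per product pair gives 3 sites per position per product per block, hence 9 of 36. The documents do not show which kind of schedule was used.

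**3. Interval half-width for one contrast, one time point.** Let σ be the residual SD, τ the SD across positions and δ the left/right difference. None is given as a design input, so all are assumed.

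- Planned model, 144 - 5 = 139 df: h0 = 1.977 × √(2/36) × √(σ² + τ² + δ²/4).
- With side (1 df) and position (3 df), 135 df: h1 = 1.978 × √(2/36) × σ × c, where c is 1 if positions are balanced within product and about 1.01 if orders are random.

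With √(2/36) = 0.2357 and c = 1.01:

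| σ, τ, δ | σ² + τ² + δ²/4 | h0 | h1 | h1/h0 | Simulated |
|---|---|---|---|---|---|
| 1.0, 0.3, 0.2 | 1.00 + 0.09 + 0.01 = 1.10 | 0.489 | 0.471 | 0.96 | 0.491 to 0.471 |
| 0.8, 0.4, 0.3 | 0.64 + 0.16 + 0.0225 = 0.8225 | 0.423 | 0.377 | 0.89 | ratio 0.89 |
| 1.0, 0.1, 0.1 | 1.00 + 0.01 + 0.0025 = 1.0125 | 0.469 | 0.471 | 1.00 | 0.468 to 0.469 |
| 1.0, 0, 0 | 1.00 | 0.466 | 0.471 | 1.01 | ratio 1.01 |

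In the first row position supplies 0.09 of the 0.10 added variance; side adds little.

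**4. Range from simulating the design** (3 blocks of 24, orders independent of product, 3,000 trials per setting, δ 0.2 to 0.3). Width ratios for τ = 0.2, 0.3, 0.4 were 0.985, 0.960, 0.925 at σ = 1.0 and 0.972, 0.935, 0.886 at σ = 0.8: about 2% to 11% narrower. A second set used σ of 0.72 and 1.10, the spread of most post-treatment SDs in the SAP's illustrative Table 8. With δ = 0.3 and τ = 0.2 the intervals were 4.5% and 1.3% narrower. With δ = τ = 0.5 they were 20% and 9.5% narrower. With no effects they were 1.2% wider.

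**5. Validity.** In the second set the planned model's mean error was within 0.01 log10. Its coverage was 94% to 96% without within-subject correlation, and 95% when 15% of sites were dropped at random. At within-subject correlations of 0.3, 0.5 and 0.7, coverage was about 96%, 97% and 97.5%, with or without side and position.

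**The case against.** The planned model follows the framework set out in the Protocol introduction, a regression of post-treatment counts corrected for baseline. The list of extra factors is open-ended, so side and position may be added. Side is balanced, since "The application will be randomized so that each treatment is used on an equal number of left and right sides of the body", and test areas are chosen to look alike. No side or position effect is documented. The study is an unpowered Phase II whose intervals are not expected to clear the targets. All of this is correct. It keeps the point small, but an optional sentence is still not a commitment to either term.

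A reader might infer that position imbalance between products is simply left to chance and distorts the estimates. The documents do not support that. Protocol 13.3 aims for the closest joint balance on all three factors, and exact position balance is feasible. What stands is narrower: position balance within product is not guaranteed, and mITT inclusion, judged separately for each side of each body area (Protocol 15.0, SAP 6.1), can disturb both balances. The precision gain does not depend on imbalance: with orders balanced within product, the simulated width ratios for the first two rows of the table were 0.952 and 0.879.

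A reader might also infer bias or a raised error rate. Step 5 shows neither; chance imbalance is already covered by the interval on average. Adding the terms at δ = 0.3 and τ = 0.2 moved a single estimate by up to 0.11 to 0.13 log10 (95th percentile). Much of that is adjustment noise, since the shift is 0.06 to 0.08 with no effects at all.

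**Conclusion.** The point holds as one about precision and prespecification. Two of the three balanced factors are missing from the primary model, and nothing in the SAP commits to including them. The cost is conditional on an effect the documents do not quantify. Under the main assumptions (σ 0.8 to 1.0, τ 0.2 to 0.4, δ 0.2 to 0.3 log10) intervals are about 2% to 11% narrower with both terms, mostly because of position. Break-even lies near τ = 0.1, and with no effect the terms cost about 1% in width. The validity of the planned intervals is not in question on this ground. Priority is low. Leaving out the subject pairing is a separate and larger gap that these terms do not repair.

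**What to change.** In SAP 7.3.1 and Protocol 7.1 and 15.1, name body side (left/right) and the randomised position of the post-treatment sample as fixed effects in the primary model for each body site and time point. Take the IP - AC and NC - IP contrasts from that model. State that any other factor, such as technician or demographics, enters only a named sensitivity analysis, so that one prespecified fit is read against the margins.

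The cost is a wording change and 4 degrees of freedom (139 to 135), with an interval about 1% wider if neither factor matters. Both variables are already in the randomisation schedule, so no new data are needed. One limit remains: the baseline count also comes from a randomised position, and these terms do not adjust for that.
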